3.0 STUDY OBJECTIVES

3.1 Primary objectives

3.1.1 CMT pilot trial

To measure the difference between oxytocin and carbetocin in changes over time in Troponin I release from baseline to 24h after test drug administration, and ECG changes from baseline to 10 minutes after test drug administration.

3.1.2 CMT2 trial

To measure the difference between oxytocin and carbetocin in changes over time in Troponin I release from baseline to an interval of 6-10h after test drug administration.

3.1.3 CMT pain trial

To measure the difference between oxytocin and carbetocin in changes over time in opioid consumption and reported pain intensity from baseline to 48h after test drug administration.

3.2 Secondary objectives

Plasma levels of sodium, hemoglobin and myocardial biomarkers such as troponin T, CK, CK-MB and NT-proBNP will be analysed for group differences in changes over time.

A study biobank is established both for the CMT pilot trial and the CMT2 trial.

To measure the difference between oxytocin and carbetocin in: uterine tone, blood loss, perioperative side effects, postoperative pain and side effects, consumption of analgesics, ECG changes, and time consumption from time of delivery till end of surgery.

To describe the relationship between the preoperative reported level of anxiety, depression and pain catastrophizing trait and opioid consumption and pain intensity during the first 48 hours after caesarean delivery.

3.3 Explorative objectives

We expect further analysis to be performed on the data set that may generate separate analysis and publications.

3.4 Study design

The study is designed as a double-blinded randomized controlled trial including healthy singleton pregnant women undergoing Caesarean delivery. The participants will be randomized 1:1 to oxytocin 2.5 U or carbetocin 100µg, 1-minute injection immediately after delivery.

3.4.1 CMT pilot trial

40 patients will be included from the birth clinics of OUH.

3.4.2 CMT2 trial

240 patients will be included from the birth clinics of OUH and AHUS.

3.4.3 CMT pain trial

40 patients from the pilot trial and the first 40 patients from the CMT2 trial included at OUH, Rikshospitalet will be included in the trial.

4.0 HYPOTHESIS AND DECISION RULES

4.1 Primary endpoint and statistical hypotheses

The protocol is designed to investigate group changes over time in patients receiving carbetocin compared to oxytocin.

The primary null hypothesis states that there is no difference between the treatment groups. The alternative hypothesis states that the changes over time differ between the treatment groups.

4.1.1 CMT pilot trial

The primary endpoint of interest is the treatment difference in changes over time in high-sensitive troponin I levels, measured at baseline 4h, 10h, and 24h after drug administration.

4.1.2 CMT2 trial

The primary endpoint is the treatment difference in changes over time in high-sensitive troponin I levels, measured at baseline and at an interval of 6-10h after drug administration.

4.1.3 CMT pain trial

The primary endpoint is treatment difference in opioid consumption and reported pain intensity within the first 48h after test drug administration.

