2.0 DATA SOURCE

2.1 Patients

We will conduct a double blinded randomized controlled trial where healthy women undergoing C-section will receive either oxytocin or carbetocin immediately after delivery of the baby. Ratio between the groups will be 1:1.

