2.1.3 CMT pain trial

This trial will include 40 patients from the pilot trial and the first 40 patients from the CMT2-trial included at the birth clinic of OUH, Rikshospitalet.

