4.2 Statistical decision rule

The primary and all secondary outcomes will be analysed with two-sided tests and confidence intervals and a statistical significance level of 5%.

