6.2.6 Postoperative pain and side effects

Pain at rest, pain after coughing, nausea and tiredness will be registered at 4h, 10h, 24h and 48 h after administration of test drug in the CMT pilot trial..

A numeric rating scale ranging from 0-10 is used (0 = no discomfort, 10 = maximal discomfort imaginable). The variables will be treated as continuous in the statistical analyses.

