6.2.7 Consumption of analgesics

Postoperative pain treatment protocol includes oral paracetamol 1 g and ibuprofen 400 mg 4 times daily and IV morphine administered by a patient controlled analgesia pump (PCA). In the CMT pain trial, overall postoperative morphine consumption in mg will be measured, as well as morphine consumption in the time periods 0-4h, 4-10h, 10-24h and 24-48h after test drug administration.

A continuous variable measured in mg.

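### The pain substudy has two primary outcomes, each tested at 5%, and no rule for combining them: the false-positive rate is up to 9.75% if either suffices, at most 5% if both are required

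*SAP*

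**What the plan says.** SAP 4.1.3 defines the endpoint: "The primary endpoint is treatment difference in opioid consumption and reported pain intensity within the first 48h after test drug administration". SAP 3.1.3 gives the matching objective, again without ranking the two outcomes: "changes over time in opioid consumption and reported pain intensity from baseline to 48h after test drug administration".

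SAP 4.2, the section on the decision rule, sets only a level: "The primary and all secondary outcomes will be analysed with two-sided tests and confidence intervals and a statistical significance level of 5" per cent. The null hypothesis in SAP 4.1 is generic and is not divided or combined by outcome: "The primary null hypothesis states that there is no difference between the treatment groups". Neither document contains an order of testing, a split of alpha or a both-required rule for this substudy.

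Neither outcome is reduced to one variable:

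- Pain, SAP 6.2.6: "Pain at rest, pain after coughing, nausea and tiredness will be registered at 4h, 10h, 24h and 48 h". That sentence goes on to limit the schedule to the pilot trial.
- Opioids, SAP 6.2.7: "overall postoperative morphine consumption in mg will be measured, as well as morphine consumption in the time periods 0-4h, 4-10h, 10-24h and 24-48h".

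On size, SAP 2.1.3 says: "This trial will include 40 patients from the pilot trial and the first 40 patients from the CMT2-trial". No power calculation is given for these 80 women. SAP 3.2 also lists postoperative pain and analgesic use among the secondary objectives, and Protocol 2.2 lists postoperative pain as secondary.

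**The concern.** A substudy with two primary outcomes needs a sentence saying what counts as a positive result. Without it, the rule can be settled after the results are known. If morphine use differs and pain does not, or the reverse, the report could call the substudy positive or negative and the SAP would not contradict either.

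The same freedom exists inside each outcome. Pain at rest or pain on coughing could each serve as the pain result, and total morphine or any of four periods as the opioid result. What is at stake is the error rate behind a claim that one drug is better for pain after caesarean delivery.

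**Working it through.** **Inputs.** Two-sided 5% per outcome (SAP 4.2). Two primary outcomes (SAP 3.1.3 and 4.1.3). Planned size 40 + 40 = 80 (SAP 2.1.3) and 1:1 allocation (SAP 2.1), taken here as 40 per arm with complete data. The correlation ρ between the test statistics is not given; 0 to 0.9 is assumed. For two-sided tests of two outcomes only its absolute size matters.

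**Step 1. The plan's own figure.** One test at 5%: 1 − (1 − 0.05) = 5.0%. This agrees with SAP 4.2 as a per-test level.

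**Step 2. Two outcomes, both nulls true.**

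Either suffices: P(either) = 1 − P(|Z₁| ≤ 1.96 and |Z₂| ≤ 1.96). With ρ = 0 this is 1 − 0.95² = 0.0975. For other ρ it comes from the bivariate normal distribution.

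Both required: P(both) = 0.05 + 0.05 − P(either).

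| Assumed ρ | Either suffices, 5% each | Both required, 5% each | Either suffices, 2.5% each |
|---|---|---|---|
| 0 | 9.75% | 0.25% | 4.94% |
| 0.3 | 9.51% | 0.49% | 4.84% |
| 0.5 | 9.07% | 0.93% | 4.65% |
| 0.7 | 8.35% | 1.65% | 4.30% |
| 0.9 | 7.04% | 2.96% | 3.62% |

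If only one null is true, a both-required claim is false only when that one test rejects, so its rate is at most 5%.

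**Step 3. More than one candidate per outcome.** With three tests (one opioid, pain at rest, pain on coughing), any one sufficing and a common correlation:

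- ρ = 0: 1 − 0.95³ = 14.3%
- ρ = 0.5: 12.5%
- ρ = 0.7: 10.9%
- ρ = 0.9: 8.4%

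**Step 4. Both required, but the pain variable left open.** Suppose morphine truly differs and is detected, while pain does not differ. A free choice between rest and coughing then gives a false both-outcomes claim with probability up to 1 − 0.95² = 9.75%. The 5% limit in Step 2 therefore depends on each outcome being one variable.

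**Step 5. What a rule restores, and its price.**

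- Holm: with both nulls true it makes a false claim only if the smaller p-value is at most 0.025. Its rate is the last column of the table, 3.6% to 4.9%. If one null is true, the rate is at most 5%.
- Price of Holm: with 40 per arm, the standardised difference detectable with 80% power is (1.960 + 0.842) × √(2/40) = 0.626 SD at 5%, and (2.241 + 0.842) × √(2/40) = 0.689 SD at 2.5%. Power at 0.626 SD falls from 80% to 71% when that outcome must pass at 2.5%.
- Price of both-required: if each test has 80% power, joint power is 0.8 × 0.8 = 64% when independent, and higher with positive correlation.

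**The case against.** The strongest objection is that SAP 4.1.3 speaks of one endpoint and joins its parts with a conjunction. That can be read as requiring both outcomes, in which case no correction is needed. A reader might infer from the two outcomes alone that the substudy's false-positive rate exceeds 5%. The documents do not support that, because it holds only if either result suffices. Nor is the 5% in SAP 4.2 a miscalculated figure: it is a level for each test and is not presented as a familywise rate. Both parts of this objection stand. What remains is that the both-required rule is nowhere stated, and that it holds the rate at 5% only once one variable per outcome is fixed (Step 4).

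A reader might also count eight pain readings and four morphine periods as twelve primary tests and arrive at 1 − 0.95¹² = 46%. The documents do not support that either. SAP 6.2.6 and 6.2.7 describe what is recorded, not twelve primary tests, and SAP 6.2.6 states its schedule for the pilot only. SAP 7.4.5 assigns linear mixed models to continuous variables with more than two time points. (It refers to 7.4.2, whose text describes regression; that is a separate wording problem.) Independence is also implausible for repeated readings in the same women.

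Finally, this is an 80-patient substudy without a power calculation, and its outcomes also appear as secondary objectives. That limits the importance of the point. It does not settle which result decides the substudy.

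**Conclusion.** The point holds as a missing decision rule. It is minor and confined to the pain substudy. If either outcome suffices, the false-positive rate is 7.0% to 9.75% for assumed correlations from 0.9 down to 0. Leaving rest and coughing pain both open raises this to between 8.4% and 14.3% over the same range. If both are required and each is a single variable, the rate is at most 5%.

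These figures assume approximately normal test statistics and, for three tests, a common correlation. CMT2 has one primary variable, troponin I, and its analysis is not touched.

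**What to change.** In SAP 4.1.3 and 4.2, before unblinding:

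1. Name one opioid variable. Total morphine over 0–48 h is one example and is already measured.
2. Name one pain variable, either at rest or after coughing, estimated over 48 h from the repeated-measures model. Confirm that its recording schedule covers the CMT2 women in the substudy as well as the pilot women.
3. State one rule: Holm across the two at an overall 5%, or both significant at 5%. Either controls the error. Neither requires ranking morphine above pain, which the documents do not do.
4. Report the other pain measure and the time-specific results descriptively, with confidence intervals.

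The change is to wording only and needs no extra patients or data. Its price is somewhat less power to claim an effect on one outcome alone under Holm, as shown in Step 5. Under a both-required rule, an effect on one outcome alone would not make the substudy positive.

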4.2 Statistical decision rule

The primary and all secondary outcomes will be analysed with two-sided tests and confidence intervals and a statistical significance level of 5%.

5.0 ANALYSIS SETS

5.1 Enrolled

The enrolled set will include healthy singleton pregnant women undergoing Caesarean delivery at the birth clinics at OUH or AHUS, who have provided informed consent and have been included into the study data base.

5.2 Full analysis set

The full analysis set will be defined as all enrolled patients randomly assigned to a treatment group having received the study drug.

The patients are included in the study at an interval of 1-14 days prior to the set date of the planned C-section. Some of the patients will go into active labor prior to the planned date, and some of the planned C-sections will be shifted to an inconvenient time point for study completion due to competing acute activity at the maternity ward. These patients will be included in the study, but will end their study participation prior to receiving the study drug. The same is true for patients requiring general anaesthesia due to inadequate effect of spinal anaesthesia.

A modified intention to treat analysis will be performed on all the patients included in the study having received the study drug.

5.3 Safety analysis set

The safety analysis set will be equal to the full analysis set.

5.4 Per protocol analysis set

The per protocol analysis set will include all randomised patients meeting the study eligibility criteria and with no major protocol deviations affecting the treatment efficacy.

Major protocol deviations include entering into active labor prior to set date of planned C-section, planned C-section shifted to an inconvenient time point for study completion due to competing acute activity at the maternity ward, and need for general anaesthesia due to inadequate effect of spinal anaesthesia.

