5.6 Protocol deviation

The following sections describe any protocol deviations that relate to the statistical analyses and forms the requirements for exclusion from the PPS.

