5.6.2 Deviations assessed post-randomization

Any patient who withdraw their consent during the observation period of 48 hours following administration of study medicine.

Randomised patients that for any medical reason will be prevented from completing the study according to study protocol.

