6.1.1 CMT pilot trial

Level of troponin I is measured at baseline and at 4, 10, 24 and if necessary 48 hours after study drug administration.

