7.4 Statistical methods

7.4.1 Primary and secondary analyses

The primary analysis will be a modified intention to treat analysis of the primary outcome (highly sensitive troponin I) on the full analysis set. We will initially perform a blinded analysis of the primary outcome.

Secondary analyses will be:

1. A per protocol analysis on the primary outcome (troponin I) on the per protocol analysis set
2. Modified intention to treat analyses of all secondary outcomes on the full analysis set
3. Sensitivity analyses to examine the impact of missing data (Section 7.4.5)

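### SAP 5.6.2 can drop women from the per-protocol troponin I analysis for events after a valid 6-10 h sample, and protocol and SAP give different randomisation times (minor)

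*SAP*

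**What the plan says.** **Per-protocol set.** SAP 5.4 opens with "The per protocol analysis set will include all randomised patients meeting the study eligibility criteria" and no major deviation affecting efficacy. It then gives an open list of three: early labour ("Major protocol deviations include entering into active labor prior to set date of planned C-section"), a section moved to an inconvenient time, and general anaesthesia after an inadequate spinal. SAP 5.2 describes the same three situations and says of the first two "These patients will be included in the study, but will end their study participation prior to receiving the study drug"; it then says the same holds for the third. The full analysis set requires receipt of study drug. SAP 5.4 does not state that requirement.

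**Further exclusions.** SAP 5.6 introduces deviations whose description "forms the requirements for exclusion from the PPS". Under 5.6.2 these are:
- "Any patient who withdraw their consent during the observation period of 48 hours following administration of study medicine"
- randomised women who "for any medical reason will be prevented from completing the study according to study protocol"

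**Use of the set.** The only per-protocol analysis listed in SAP 7.4.1 is "A per protocol analysis on the primary outcome (troponin I) on the per protocol analysis set". SAP 6.1.2 measures troponin I in CMT2 at baseline and once at 6-10 h.

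**Randomisation time.** Protocol 10.2 initiates randomisation when the woman is first registered in the eCRF, and protocol 12.3 has randomisation follow consent. SAP 7.2 places it after inclusion and just ahead of study start, a term it does not define. SAP 5.2 puts inclusion 1-14 days before the planned section. Protocol 6.4.1 replaces women lost before randomisation and says nothing on replacing later losses. SAP 5.5 reports women randomised but not treated on the flowchart and nowhere else.

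**The concern.** A per-protocol analysis of one laboratory value should exclude women whose treatment or measurement departed from the protocol. Withdrawal or a medical event after the sample changes neither. In a cardiac-safety trial, a later medical problem is also an unwelcome reason to discard a troponin value, because the problem may be related to what the value measures. Selecting on events after the endpoint makes any difference between the per-protocol and primary results harder to interpret.

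The two randomisation times matter because the SAP itself expects exits before dosing. Whether those women had been allocated decides whether they are replaced, whether they appear as untreated losses, and what the target of 240 refers to.

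**Working it through.** **1. Exclusion window against endpoint window (CMT2).**
- Withdrawal exclusion (SAP 5.6.2): 0 to 48 h after study drug.
- Last sample needed for the endpoint (SAP 6.1.2): between 6 h and 10 h.
- Sampled at 10 h: 48 - 10 = 38 h of the window remain (38/48 = 79%).
- Sampled at 6 h: 48 - 6 = 42 h remain (42/48 = 88%).

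So for 38 to 42 of the 48 hours, a withdrawal removes a woman whose endpoint is complete. The medical-reason clause has no time limit of its own. On a plain reading, completing the study includes the 48 h follow-up, so an event at 30 h could remove a complete endpoint too. These are spans of time, not expected numbers of women; the documents give no rate for either event.

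**2. Is the per-protocol set a subset of the full analysis set?**
- Full analysis set: randomised and dosed.
- Per-protocol set: randomised, eligible and without a major deviation; dosing is not stated.

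The three deviations named in 5.4 remove undosed women from the randomised denominator. A woman who withdraws before dosing for some other reason is not named in 5.4. The consent clause of 5.6.2 does not reach her either, since its period begins at study drug. With no follow-up sample she would not alter the estimate, but she could enter the stated size of the set.

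**3. The two randomisation times, for a woman who goes into labour before her planned date.**
- Allocated at first eCRF registration (protocol 10.2): she is already randomised. Protocol 6.4.1 does not provide for her replacement, and SAP 5.5 shows her as randomised but not treated. If registration and allocation coincide, 240 registered and 240 randomised are the same count.
- Allocated just before surgery (one reading of SAP 7.2): she is not yet randomised. Protocol 6.4.1 replaces her, and she is not a post-randomisation loss. SAP 7.1.2 enrols 240, and SAP 5.1 defines enrolled as consented and in the database. With replacement, however, 240 would have to count randomised women.

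A failed spinal, or a section moved on the day, could follow allocation under either reading.

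**4. Does this threaten the sample size?** The plan's figure reproduces. Inputs from SAP 7.1.2 and 4.2: SDs of change 0.79 and 4.48, difference 1.37 ng/L, two-sided 5%, t-test for unequal variances. With 89 per arm:
- Standard error = sqrt(0.79²/89 + 4.48²/89) = sqrt(0.00701 + 0.22551) = 0.482.
- Noncentrality = 1.37/0.482 = 2.84; Satterthwaite df about 93.
- Power = 80.3%, and 89 is the smallest number per arm reaching 80%, so 178 in total.

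The allowance is 240 - 178 = 62 women, or 62/240 = 25.8%. No exit rate is stated, so nothing shows the allowance will be exceeded. This step does not measure the per-protocol problem, which leaves the primary analysis untouched.

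**The case against.** The strongest reply is that excluding women who do not complete the protocol is an ordinary per-protocol choice, that it touches one secondary analysis, and that the SAP expects few drop-outs and little missing data. The documents also do not say whether samples taken before a withdrawal may be used. All of this stands, and it keeps the point small. It does not justify a rule that ignores whether the only endpoint analysed in that set has been obtained.

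Several stronger readings are tempting, but the documents do not support them:
- *The list in SAP 5.4 is empty or contradictory.* The three named deviations remove nobody from the full analysis set. But 5.4 starts from all randomised women, and there the list does real work. It is also open-ended.
- *The 48 h limit is left over from the pilot.* For the pilot, SAP 6.1.1 does say "Level of troponin I is measured at baseline and at 4, 10, 24 and if necessary 48 hours after study drug administration". But 5.6.2 refers to the observation period, and 48 h is the follow-up of the whole trial (protocol section 4, SAP 2.3).
- *SAP 7.2 intends allocation on the day of surgery.* This is not established. SAP 5.4 treats labour before the planned date as a deviation among randomised women, and SAP 5.5 plans for women randomised but untreated. Both fit earlier allocation, as in protocol 10.2.
- *A sample outside 6-10 h is a defect in the primary analysis.* No explicit rule exists, but the endpoint is defined by that window, so such a value can be read as missing under the complete-case rule of SAP 7.4.5. This is a clarification only.

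**Conclusion.** The point holds on two counts, and its severity is minor. First, SAP 5.6 with 5.6.2 is a stated rule that can discard complete troponin I data for events after the sample, in a set used for nothing else. Second, protocol 10.2 and SAP 7.2 differ on when women are allocated, so expected pre-dose exits are handled differently depending on which text is followed.

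The effect is confined to one secondary analysis and to the accounting of women who leave before dosing. A reader might infer bias or lost power in the primary analysis; neither is shown. The primary analysis uses the full analysis set, these exits precede dosing, and allocation is hidden from the study team apart from the syringe preparer and the person who generates the list. The conclusion assumes a plain reading of two loose terms, initiated in protocol 10.2 and study start in SAP 7.2, and that completing the study means completing the 48 h follow-up.

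**What to change.** 1. In SAP 5.6.2, for CMT2, limit the withdrawal and medical non-completion exclusions to events before the 6-10 h sample, as far as consent allows use of the data. In SAP 5.4, require receipt of study drug, so that the per-protocol set is a subset of the full analysis set. Both are wording changes with no new data collection.
2. Reconcile protocol 10.2 and SAP 7.2 on one allocation time, define study start, and state whether 240 counts registered or randomised women. Aligning SAP 7.2 to protocol 10.2 is cheaper, but leaves pre-surgery exits as post-randomisation losses. Allocation close to surgery would reduce those losses, though not remove them all. It would need some extra registrations and, because protocol 10.2 would change, an amendment approved by the medicines agency and the ethics committee (protocol 11.2).
3. While amending, add a sentence on how a troponin sample outside 6-10 h is handled in the primary and per-protocol analyses. This is a clarification and costs only wording.
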